15.13.7 Safety Monitoring

For this sub-study, only serious adverse event (SAE) e.g., related to procedural complications during blood sampling have to be collected. Study centers and Investigators are instructed to report all SAEs to MorphoSys Drug Safety ([contact]) within 24 hours, using the sub-study specific SAE report form. Note: Follow up of SAEs also have to be reported within 24 hours.

For definitions please refer to Section 10 of the study protocol.

15.13.8 Study Management and Data Handling

Source documents are considered to be all information within original records and covered on certified copies of original records concerning clinical findings, observations, data or other activities in the clinical sub-study necessary for the reconstruction and evaluation of the sub-study.

The sub-study will be monitored to ensure that it is conducted and documented properly according to the protocol, GCP, and all applicable regulatory requirements.

All patients will be informed that participation is entirely voluntary and will have to sign the Informed Consent Form (ICF). Patient must consent to the sub-study before or on first sub-study visit, before blood sample collection of the sub-study. The Investigator will inform any patient participating in the sub-study that this sub-study protocol explicitly allow to undergo any medical treatment including anti-neoplastic therapy for their disease as necessary.

The required data for the sub-study will be collected on the Sub-Study specific Laboratory Requisition Form. These data will not be entered in the eCRF of the main study. Data entered on the Laboratory Requisition Form should be consistent with the source documents, or the discrepancies must be explained.

The primary method of data transmission is via the sub-study specific Laboratory Requisition Form transferred to Central laboratory together with the laboratory samples collected. The data collected on the Laboratory Requisition Form will be transferred to the laboratory database.

The Central laboratory will be responsible for the processing and the quality control of the data collected for the sub-study according to standard operating procedures (SOPs) and sub-study specific procedures.

Queries will be handled via paper based Data Clarification Forms.

All study forms and records transmitted to the Central Laboratory/sponsor must just carry coded identifiers such that personally identifying information is not transmitted.

For further general rules and guidelines applicable regarding study management please refer to Section 13 of the study protocol.

15.13.9 Sub-Study Statistical Methods and Planned Analyses

The analysis will be conducted after completion of the sub-study and reported as an addendum to the Clinical Study Report covering the final analysis of the main study.

Descriptive statistics summarizing CD19 expression levels on peripheral B cells (CLL and normal B cells) will be calculated by visit, respectively. The following will be derived:

- Absolute levels by visit including sub-study visits.
- Relative change from baseline of the main study by sub-study visits.
- Relative change from the “End of Treatment Visit” by sub-study visit.

Descriptive statistics summarizing genetic CD19 mutations and alternative CD19 splice variants in peripheral B cells (CLL and normal B cells) will be calculated by visit, respectively. The following will be derived:

- Proportion of patients with acquired CD19 mutation(s) during the MOR00208 treatment period
- Proportion of patients with detectable alternative CD19 splice variants

CD19 mutational status and alternative CD19 splice variants will be summarized. No formal statistical testing will be conducted. Further details will be specified in the SAP.

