	
Patients will self-administer the dose of 150 mg twice daily orally continuously during the study duration.
 
Venetoclax dose: To mitigate the risk for tumor lysis syndrome (TLS), treatment of patients with venetoclax will be initiated at 20 mg up daily dose from Cycle 1 Day 8 (C1D8) for 7 days, followed by a weekly ramp-up dosing schedule (50 mg, 100 mg, 200 mg daily dose) to the recommended daily dose of 400 mg, starting from C2D8. Patients will self-administer venetoclax throughout the study duration except during hospitalization.

Study Participation Duration	
Treatment with MOR00208 and idelalisib or venetoclax will continue until disease progression. If a compound specific adverse reaction occurs that requires the discontinuation of MOR00208, idelalisib or venetoclax the other therapy will be continued until progression of disease, withdrawal of consent, unacceptable toxicity, death or patient being lost to follow-up, whichever occurs first.
 
The duration of the main study is limited to a maximum of 5 years in total. Patients who have not progressed at the end of the treatment period (after 24 treatment cycles) or at the end of the total study duration may continue with MOR00208 treatment upon Investigator's discretion.

Supply, Preparation and Administration	
MOR00208 DP is a lyophilisate supplied in single-use 20 mL glass vials. Each vial contains 200 mg of MOR00208 for reconstitution with 5 mL of water for injection. Reconstitution yields 40 mg/mL MOR00208 in 25 mM sodium citrate, 200 mM trehalose and 0.02% (w/v) polysorbate 20 at pH 6.0. Each product vial is intended to deliver 200 mg of MOR00208 in 5 mL of reconstituted solution. MOR00208 will be diluted into a 250 mL infusion bag containing 0.9% (w/v) sodium chloride for injection.
 
Idelalisib 100 and 150 mg film-coated tablets in bottles of 60 tablets, as commercially available.
 
Venetoclax 10 mg, 50 mg and 100 mg film-coated tablets as commercially available for oral administration.

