4.5.2 Clinical Experience with MOR00208 in CLL

Protocol XmAb5574-01:

A Phase 1 Study of XmAb[®]5574 to Evaluate the Safety, Tolerability, and Pharmacokinetics in Patients with Relapsed or Refractory Chronic Lymphocytic Leukemia

The first study in humans was a phase I trial exploring the use of MOR00208 (also known as XmAb[®]5574 or MOR208) in adult patients diagnosed according to International Workshop on CLL guidelines (Hallek et al., 2008) with active, treatment-requiring R/R CLL/SLL. Results of the study were reported by Woyach et al. (2014a).

Twenty-seven patients were enrolled to 6 escalating dose levels, with expansion at the highest dose level of 12 mg/kg. Nine doses of MOR00208 were infused over 8 weeks. The maximum tolerated dose (MTD) was not reached; the drug was generally well tolerated, IRRs of grade 1 or 2 being the most common toxicities. Treatment-related grade 3 or 4 AEs occurred in 5 patients and included neutropenia, thrombocytopenia, increased aspartate aminotransferase (AST), febrile neutropenia, and tumor lysis syndrome (TLS). MOR00208 showed preliminary efficacy, with 18 patients (66.7%) responding by physical examination criteria and laboratory studies, and 8 patients (29.6%) responding by computed tomography (CT) criteria. MOR00208 showed a terminal elimination half-life of approximately 14 days. A dose of 12 mg/kg was recommended for use in subsequent studies.

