9.2.9 End of Treatment Visit

Patients will continue on study treatment until documented disease progression, intolerable toxicity, withdrawal of consent to continue study treatment, death, physician decision or early termination of the study. At that time, an End of Treatment (EOT) visit will be performed.

Assessments are to be completed preferably within ≤ 30 days of last study medication intake. The EOT visit will involve:

- Documentation of concomitant medications
- Blood sampling B-/T-/NK-cell count, CD19 expression assessment (see Section [9.3.6](#)), for anti-MOR00208 antibodies (Section [9.3.5](#)), MOR00208 PK sample (see Section [9.3.4](#)) and a MRD assessment (only in case of CR or PR; see Section [9.3.3.6](#))

- Disease response assessment of CLL and SLL (CT or MRI scans of neck, chest, abdomen, pelvis)
- Bone marrow aspiration and biopsy (**required** for confirmation of CR)
- B-symptoms (see Section 9.3.3.5)
- Serum pregnancy test for FCBP (see Section 9.3.2.1)
- ECOG performance status (see Section 0)
- Blood sampling for hematology, serum chemistry and coagulation (central laboratory) (see Section 9.3.2.5)
- Urinalysis (see Table 11)
- Complete physical examination (see Section 9.3.2.3)
- Vital signs and weight (see Section 9.3.2.2)
- 12-lead resting ECG (see Section 9.3.2.4)
- Recording of (S)AEs (see Sections 10.2 and 10.5)

Assessments can take place within 7 days of the actual EOT visit.

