15.13.2 Sub-Study Objectives and Endpoints

15.13.2.1 Study Objectives

- To assess potential downregulation/loss of CD19 on peripheral B cells (CLL and normal B cells) as escape mechanism to MOR00208 treatment
- To assess the kinetics of CD19 recovery on peripheral B cells (CLL and normal B cells) after MOR00208 treatment discontinuation, if applicable
- To assess MOR00208 serum concentrations as supportive parameter for CD19 expression analysis

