15.13.6 Sub-Study Procedures

15.13.6.1 Schedule of Procedures and Assessments

The Schedule of Procedures and Assessments is presented on the following page (Table 15). All assessments that need to be performed at a specific visit are indicated with an "X".

Note: Any visit performed not in the visit window as described in Table 15 will be not considered as protocol deviation.

MorphoSys AG Proprietary Information

Table 15: Sub-Study - Schedule of Procedures and Assessments

Procedure	Sub-Study Period			
	Visit 1 ^{1,2}	Visit 2 ²	Visit 3 ²	Visit 4 ²
	~30 days after EoT of the Main Study ¹	~1 month after Visit 1 ±2 weeks	~3 months after Visit 1 ±6 weeks	~6 months after Visit 1 -6 weeks/+ ≥6 weeks
Informed consent	X ³	(X) ³	(X) ³	(X) ³
CD19 assessment (CD19ABC) (blood)	X	X	X	X
Optional analysis of genetic CD19 mutations (blood)	X	X	X	X
Optional analysis of alternative CD19 splice variants (blood)	X	X	X	X
PK MOR00208 (serum)	X	X	X	X
Concomittant anti-tumor therapy	X	X	X	X
SAE (Serious Adverse Event) related to blood sampling	X	X	X	X

¹ Patient should return for Visit 1 of the sub-study within approximately 30 days after end of treatment visit (EoT) of the main study. **Note:** Visit 1 could be on the same day of the 30 day safety follow-up (SFU) visit of main study.

² Alternatively, for those patients who already completed the main study before implementation of the sub-study, the visit(s) will be scheduled after ~2 months from EoT of the main study for Visit 2, after ~4 months for Visit 3 and after ~7 months for Visit 4 as applicable. **Note:** These patients may have less visits than as per regular schedule (e.g., only 1 visit if patient completed the main study more than 7 months before enrolment in the sub-study).

³ Patient must consent to the sub-study before or on first sub-study visit, before blood sample collection of the sub-study. (X) is applicable for those patients who already completed the main study before implementation of the sub-study.

Abbreviations: ABC= Antibodies bound per cell; EoT= End of Treatment visit of the main study

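### The sub-study tabulates CD19 by visit label rather than by time since the last MOR00208 infusion, so recovery kinetics cannot be read reliably from the planned tables

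*Protocol*

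**What the plan says.** Protocol 15.13.2.1 sets the objective: "To assess the kinetics of CD19 recovery on peripheral B cells (CLL and normal B cells) after MOR00208 treatment discontinuation, if applicable". Section 15.13.1 explains that CD19 may be internalised under MOR00208, that its recovery is unknown, and that the four sub-study visits were chosen with falling serum drug levels in mind.

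For the analysis, 15.13.9 says: "Descriptive statistics summarizing CD19 expression levels on peripheral B cells (CLL and normal B cells) will be calculated by visit, respectively". The derived quantities are absolute levels by visit, relative change from main-study baseline, and "Relative change from the “End of Treatment Visit” by sub-study visit". It leaves further detail to the SAP.

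The visit clock is built as follows:

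- **EoT.** Section 9.2.9: "Assessments are to be completed preferably within ≤ 30 days of last study medication intake". This refers to either drug. The Synopsis adds: "If a compound specific adverse reaction occurs that requires the discontinuation of MOR00208, idelalisib or venetoclax the other therapy will be continued". Sections 8.4 and 8.11 likewise let MOR00208 stop while the partner drug goes on.
- **Visit 1.** About 30 days after EoT in the Table 15 header; within about 30 days in footnote 1 and in 15.13.1.
- **Visits 2, 3 and 4.** About 1, 3 and 6 months after Visit 1, with windows of ±2 weeks, ±6 weeks, and minus 6 weeks with no upper limit. Off-window visits do not count as deviations.
- **Patients who had already finished the main study.** Visits are set directly from EoT and may be fewer: "only 1 visit if patient completed the main study more than 7 months before enrolment in the sub-study".

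Serum MOR00208 is sampled with CD19 at every sub-study visit.

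**The concern.** Recovery after a drug is withdrawn runs on a clock that starts at the last infusion. The planned summaries use a clock that starts at EoT, or at a visit that depends on EoT. If the gap between last infusion and EoT varies between patients, and the visit windows add further spread, a median at one visit label averages patients at different points of washout. A label with a higher number may then hold samples that are earlier in washout than some under the label before it.

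The change from EoT has a related problem. In a patient whose MOR00208 stopped well before the partner drug, the EoT sample may already show recovered CD19, and a flat change afterwards would look like an absence of recovery. Each cohort has about 12 patients and the sub-study is optional, so one or two such patients can move a median.

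**Working it through.** **Inputs.** Half-life, from Protocol 4.5.2: "MOR00208 showed a terminal elimination half-life of approximately 14 days". EoT is taken as 0 to 30 days after the last infusion (MOR00208 as the last drug, 9.2.9 preference met). Visit offsets and windows come from Table 15. One month = 30.4375 days.

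**Reproducing the plan's own figure.** Visit 1 at about 1 month after EoT, plus 1, 3 and 6 months, gives 2, 4 and 7 months after EoT. This agrees with Table 15, footnote 2.

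**Formulas.**

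- Days since last infusion = (infusion to EoT) + (EoT to Visit 1) + (Visit 1 to visit, with its window).
- Fraction of drug remaining = 2^(−days/14).

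**Visit 1 exactly 30 days after EoT.**

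| Label | Days since last infusion | Drug remaining | Spread |
|---|---|---|---|
| EoT | 0 to 30 | 100% to 22.6% | 4.4-fold |
| Visit 1 | 0+30 to 30+30 = 30 to 60 | 22.6% to 5.1% | 4.4-fold |
| Visit 2 | 30+30.4−14 to 60+30.4+14 = 46 to 104 | 10% to 0.57% | 18-fold |
| Visit 3 | 30+91.3−42 to 60+91.3+42 = 79 to 193 | 2.0% to 0.007% | about 280-fold |
| Visit 4 | 30+182.6−42 = 171, to 285 if cut at +6 weeks (upper end open) | at most 0.02% | elapsed time only |

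**Visit 1 anywhere from 0 to 30 days after EoT** (the footnote 1 reading). Visit 1 covers 0 to 60 days (100% to 5.1%, about 20-fold). Visit 2 covers 16 to 104 days (78-fold), Visit 3 covers 49 to 193 days, and Visit 4 starts at 141 days (141/14 = 10 half-lives, about 0.1% remaining).

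**Overlap.** Visit 1 reaches day 60 and Visit 2 starts at day 46 (16). Visit 2 reaches day 104 and Visit 3 starts at day 79 (49). Visit 3 reaches day 193 and Visit 4 starts at day 171 (141). Figures in brackets use the second reading.

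**Windows alone.** With EoT on the day of the last infusion and Visit 1 exactly 30 days later, Visit 2 still covers 46 to 74 days (4-fold) and Visit 3 covers 79 to 163 days (64-fold).

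**MOR00208 stopped k cycles before the partner drug** (k is an assumption). Add 28k days. Visit 1 becomes 58 to 88 days for k = 1, 114 to 144 for k = 3, and 198 to 228 for k = 6. The EoT sample moves by the same amount.

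**The case against.** The case against has several parts.

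- **Down-regulation does not depend on EoT timing.** CD19 is measured at C1D1, on treatment (C2D1 in Cohort A; C1D8 and C1D15 in Cohort B) and at EoT. The change from main-study baseline does not use EoT as its reference. This stands: a reader might infer that down-regulation cannot be detected at all, and the documents do not support that.
- **Drug level is measured alongside CD19.** Section 15.13.2.1 names it as support for the CD19 analysis, and a measured concentration is better than one inferred from a half-life. This also stands. The data can answer the question, but 15.13.9 does not say how the two will be brought together.
- **Visit 1 can be well timed.** Footnote 1 allows it on the day of the 30-day safety visit, which falls 30 days after the last dose. If MOR00208 was the last drug, that puts Visit 1 near day 30. This is an option, and the later windows remain.
- **Visit 4 does not mix patients with and without drug.** At most about 0.1% remains there in every scenario above, so the open window affects elapsed time only. This stands.
- **Long gaps are hypothetical.** A six-cycle gap (168 days, or 168/14 = 12 half-lives before EoT) is permitted, but nothing in the documents gives its frequency or length. It serves only as an illustration.
- **Detail is left to the SAP, and the kinetics objective is conditional.** The SAP supplied is based on protocol Version 10.0 and contains nothing on the sub-study, so its silence proves little. Its general rule (SAP 4.1.4) is to use nominal visits without re-windowing by date, which would not help if carried over. For main-study PK, SAP 4.9.2 excludes samples taken outside their day window from summaries, so the principle that timing matters is already accepted.
- **The sub-study is exploratory and descriptive.** It has no testing and does not bear on the main study's primary or secondary endpoints. This limits the importance of the point.

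**Conclusion.** The point holds in limited form. The stated analysis describes CD19 by labels that do not measure time since MOR00208 was stopped, and recovery kinetics cannot be read reliably from those tables. Residual drug under one label varies 4.4-fold at Visit 1 (about 20-fold on the looser reading) and 18-fold at Visit 2 (78-fold), and neighbouring labels overlap. An earlier stop of MOR00208 alone would widen this and could make EoT an already recovered reference.

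It would go too far to call the sub-study data uninterpretable. Infusion records, sample dates and paired concentrations allow the right analysis; what is missing is a plan to do it. It would also be wrong to say that every visit is counted from EoT: in the regular schedule only Visit 1 is.

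The figures assume simple exponential decline at the phase I half-life and EoT within 30 days of the last infusion, which the protocol only prefers. Actual timings are not in the documents. I rate this a cheap improvement.

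**What to change.** In 15.13.9 and in the sub-study SAP:

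1. Make the main kinetics display a per-patient plot and listing of CD19 ABC against actual days since the last MOR00208 infusion. Include EoT and sub-study samples, with baseline and on-treatment samples shown before day zero. Pair each value with the serum MOR00208 concentration from the same visit where one was taken.
2. When reporting change from EoT, flag patients whose last infusion was well before EoT, using a threshold fixed in advance.
3. Keep the by-visit tables as secondary.

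Do not replace the labels by fixed bins of days. Bins of up to 45, 46 to 90 and 91 to 180 days would span 2^(45/14) = 9.3-fold, 2^(44/14) = 8.8-fold and 2^(89/14) = 82-fold in residual drug. The first two are wider than the 4.4-fold spread at Visit 1 and the third is far wider. A bin above 180 days would be open-ended, and with so few patients some bins might be nearly empty. Individual plots avoid this.

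The cost is a few extra outputs and a data merge. Sub-study data sit in a laboratory database outside the main eCRF (15.13.8), whereas MOR00208 administrations are recorded in the eCRF (8.12), so infusion dates must be linked by patient. Change from main-study baseline already needs sub-study patients to be linked to their main-study data. No new visit or sample is required.

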7.4 End of Study and Subsequent Treatment

The end of the main study is reached for an individual patient, if any of the following applies:

- Patient has withdrawn consent (see Section 7.2.3)
- Patient has completed 30-Day Safety Follow-up visit
- Study treatment was permanently discontinued (see Section 7.2.4)

The individual end of the main study is defined by the above criteria, whichever occurs first.

The end of the main study is defined as 5 years after the first patient was enrolled (C1D1) or approximately 30 days after last patient received his last treatment, whichever comes first. The whole study will end after the completion of both the main and sub-study (see for details in Section 12.11 and 15.13.5). At the end of the study, access to MOR00208 treatment can be made available to those patients who continue to derive benefit from MOR00208 treatment.

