12.1 Determination of Sample Size

The primary endpoint of this study is the incidence and severity of AEs in Cohort A (MOR00208 combined with idelalisib) and Cohort B (MOR00208 combined with venetoclax) and will be analyzed descriptively. In each cohort 12 patients will be enrolled. No formal sample size calculation was performed and no formal statistical hypothesis testing is planned.

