15.13.1 Sub-Study Purpose/Rationale

It is of importance and has high clinical value to better understand potential escape mechanisms to MOR00208 treatment and to evaluate whether subsequent CD19-targeting therapeutic options can be offered to patients after MOR00208 treatment. Subsequent CD19-targeting therapy may include novel chimeric antigen receptor (CAR) T-cell therapy, other anti-CD19 targeting antibodies than MOR00208, or potential re-challenging with MOR00208 e.g. after drug holiday as shown for another antibody (Zou Y et al., 2018; Alici E et al., 2016).

It is well described that resistance to targeted antibody treatment could potentially be mediated by alterations in expression of the target antigen as shown in a preclinical Burkitt's lymphoma cell line model where down-modulation of CD20 as well as clonal selection of CD20-negative cells was related to the acquired resistance to rituximab (Smith MR, 2003; Takei K et al., 2006).

For the antigen CD19, emerging data from CD19 targeted CAR T-cell trials in B-cell malignancies demonstrate that a common mechanism of resistance to therapy is the emergence of tumors with loss or downregulation of CD19 antigen via mechanisms like alternative mRNA splicing, CD19 gene deletion and mutation or CD19-negative clonal evolution (Zheng PP et al., 2018; Zhao Z et al., 2018). A recently published Brief Communication paper (Orlando EJ, 2018) underlines that acquired resistance to CD19-targeted CAR T-cell therapy in acute lymphoblastic leukaemia can occur through mutations in the CD19 gene, consequently leading to the loss of CD19 antigen surface expression on tumor cells.

In a Phase I trial (NCT01161514), where relapsed/refractory CLL/SLL patients received MOR00208 treatment, CD19 expression was evaluated, but due to methodological limitations (MOR00208 interference with anti-CD19 detection) the obtained data do not allow proper interpretation of CD19 expression levels during and after the treatment period.

To accurately address CD19 antigen expression during MOR00208 treatment, a validated method for quantitative CD19 assessment was implemented in the COSMOS trial to evaluate samples collected at Cycle 1 Day 1 (baseline value), during treatment at Cycle 2 Day 1 in Cohort A or Cycle 1 Day 8 & 15 in Cohort B, furthermore, at the end of treatment visit (EOT).

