15.13.3 Sub-Study Design

15.13.3.1 Description of Sub-Study design

This is an optional sub-study subsequent to the main study in which biological samples will be collected for investigations on biological markers (e.g., CD19 expression) for CLL disease. Patients who completed the main study will be invited to participate in this optional sub-study. Patients who provided their voluntary consent to participate in the sub-study will have additional blood samples collected as detailed in Section 15.13.6 below. During the participation in the sub-study patients could receive anti-neoplastic therapy for their disease.

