4.8 Efficacy Analysis

4.8.1 Secondary Endpoint

Single efficacy variable analyzed in this study is: **Best Objective Response Rate (ORR)**

(Best) ORR is defined for Cohort A as percentage of patients achieving a complete response (CR), a partial response (PR) or a partial response with lymphocytosis (PRL) at any time during the study, and for Cohort B as percentage of patients achieving a CR or a PR at any time during the study based on the local assessment. CR, PR or a PRL is defined according to the criteria of the International Workshop on Chronic Lymphocytic Leukemia (IWCLL) for CLL patients (Hallek et al., 2008; see Section 6.3), with the modification that treatment-related lymphocytosis in the absence of other signs or symptoms of disease progression will not be considered as progressive disease (Cheson et al., 2012; Hallek et al., 2012; NCCN NHL 2015 Guidelines). For patients with SLL, assessments will be performed using the Lugano Classification criteria for SLL patients (Cheson et al., 2014). The number of patients and rates will be reported split by cohort.

For derivation of the best ORR, response assessments after a patient has started a new anti-neoplastic therapy will not be taken into account.

Response evaluations (CR, PR, PRL, SD and PD) will be tabulated with counts and percentages for each available visit. Missing response evaluations, or non-evaluable assessments will be taken into account, with patients with missing responses included in the denominator for calculating rates.

The above summary/analysis will be performed using the FAS and PPS.

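### CD19 mutations 'acquired' during MOR00208 treatment cannot be dated from the scheduled samples, and the sub-study's CD19 summaries do not separate samples taken after later therapy

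*Protocol*

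**What the plan says.** The optional sub-study (Protocol Appendix M, 15.13) has two main aims: to see whether CD19 loss is a route of escape from MOR00208, and to describe how CD19 recovers once MOR00208 stops (15.13.2.1).

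- **Planned analysis (15.13.9).** CD19 levels by visit, relative change from main-study baseline and from EoT, and two proportions. One of these is "Proportion of patients with acquired CD19 mutation(s) during the MOR00208 treatment period". The section closes: "No formal statistical testing will be conducted. Further details will be specified in the SAP".
- **Later therapy (15.13.3.1).** "During the participation in the sub-study patients could receive anti-neoplastic therapy for their disease". Section 15.13.8 repeats the permission for any medical treatment. Table 15 records concomitant anti-tumour therapy at all four visits.
- **Possible next treatments (15.13.1).** The rationale says that later CD19-directed treatment may include CAR T-cells, other anti-CD19 antibodies or re-challenge with MOR00208. Of CD19 CAR T-cell trials it says that "a common mechanism of resistance to therapy is the emergence of tumors with loss or downregulation of CD19 antigen", with gene mutation among the mechanisms.
- **Further MOR00208 (7.4).** When the study closes, "access to MOR00208 treatment can be made available to those patients who continue to derive benefit from MOR00208 treatment".
- **Late entrants (Table 15, footnote 2).** Patients who left the main study before the sub-study opened join at about 2, 4 or 7 months after EoT. The footnote adds: "These patients may have less visits than as per regular schedule (e.g., only 1 visit if patient completed the main study more than 7 months". The interval meant is the one up to joining the sub-study.
- **SAP 4.8.1.** For best response, "response assessments after a patient has started a new anti-neoplastic therapy will not be taken into account". The SAP has no corresponding rule for CD19 and no sub-study section.

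**The concern.** A measure of mutations acquired during treatment needs a sample before treatment and one at its end. The schedule supplies the first, if the patient agrees to it, but not the second. The interval in which a mutation could have arisen therefore runs past the end of MOR00208, by an amount that differs between patients.

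That off-treatment interval is also when patients may start other therapy. The protocol itself describes CD19-directed treatment as a cause of CD19 loss and mutation. If such a patient's sample enters the same by-visit summary as everyone else's, the table cannot show whether the change followed MOR00208 or what came after it. The sub-study is meant to inform whether CD19-directed treatment remains an option after MOR00208, so this is the distinction its tables need to preserve.

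**Working it through.** The plan gives no sub-study sample size, rate or power, so there is no figure to reproduce. The check is of schedule against endpoint, followed by an illustration of size.

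**1. Where CD19 genetic blood is scheduled**

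| Time point | CD19 expression | CD19 mutation | Source |
|---|---|---|---|
| C1D1 | yes | optional | Protocol Table 10 |
| On treatment | Cohort A: C2D1; Cohort B: C1D8, C1D15 | none | Protocol Table 10 |
| EoT | yes | none | Protocol Table 10; 9.2.9 |
| Sub-study Visits 1 to 4 | yes | optional | Protocol Table 15 |

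Protocol 9.3.6 lists CD19 genetic analysis among assays that may be done at baseline and during the study, but no post-baseline time point is scheduled for it.

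**2. What a newly found mutation can be dated to**

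- Regular schedule: Visit 1 is about 30 days after EoT, and EoT is preferably within 30 days of the last dose. The sample can fall up to about 30 + 30 = 60 days after the last dose.
- Late entrants: the first sub-study sample is about 2, 4 or 7 months after EoT, or later.
- Without a C1D1 genetic sample, a mutation cannot be called acquired at all.

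In every case the interval from C1D1 to first detection contains the treatment period but ends after it. The named measure cannot be derived as worded.

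**3. Whether anything separates samples by later therapy**

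- Eligibility (15.13.4) excludes only patients with less than one cycle of MOR00208. It does not address therapy started since.
- 15.13.9 has no rule that excludes, flags or splits samples after new therapy or renewed MOR00208.
- MOR00208 serum level is measured at each visit as a supportive parameter (15.13.2.1). It could reveal renewed MOR00208, but no rule for using it is given, and it says nothing about other therapies.
- The supplied SAP is based on protocol Version 10.0 of 25 July 2017, while the sub-study rationale cites 2018 papers. The SAP therefore appears to predate the sub-study.

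**4. Size (illustration)**

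Protocol 12.1 gives the ceiling: "In each cohort 12 patients will be enrolled. No formal sample size calculation was performed and no formal statistical hypothesis testing is planned". That is at most about 2 × 12 = 24 patients. One patient whose mutation arose after later therapy moves the proportion by 1/n (exact Clopper-Pearson intervals):

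| Evaluable n | 0 patients | 1 patient | Shift |
|---|---|---|---|
| 12 | 0% (95% CI 0 to 26.5) | 8.3% (0.2 to 38.5) | 8.3 points |
| 24 | 0% (0 to 14.2) | 4.2% (0.1 to 21.1) | 4.2 points |

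The documents give no time to next therapy. Assuming an exponential time with median m months from EoT, the share on any new therapy by month t is 1 − 2^(−t/m):

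| Assumed m | Visit 1 (t = 1) | Visit 2 (t = 2) | Visit 3 (t = 4) | Visit 4 (t = 7) |
|---|---|---|---|---|
| 3 | 21% | 37% | 60% | 80% |
| 6 | 11% | 21% | 37% | 55% |
| 12 | 6% | 11% | 21% | 33% |
| 24 | 3% | 6% | 11% | 18% |

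These shares cover any new therapy and ignore deaths. How much of it would be CD19-directed is not stated anywhere.

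**The case against.** **Details are deferred to a SAP.** This stands. The supplied SAP does not cover the sub-study, and a later one may add the rule. It limits the claim to what could be reported, but does not rescue the mutation measure, whose wording conflicts with a schedule that is already fixed.

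**By-visit reporting shows the timing.** This is partly right. A patient negative at Visit 1 and positive at Visit 4 is visibly a post-treatment case. It does not help a patient first sampled at 4 or 7 months, or one positive at the first sub-study sample.

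**The data for a split are collected.** Therapy is recorded at every visit, but on a Laboratory Requisition Form outside the eCRF (15.13.8), and Table 15 does not show that start dates are captured.

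**Section 7.4 may mean access after the whole study.** That reading is possible, because the sentence follows the definition of the end of both main study and sub-study. The point does not depend on it: 15.13.1 names re-challenge as a possibility and 15.13.8 allows any treatment.

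**Cutting at new therapy is informative.** This stands and shapes the fix. Patients treated early are the relapsing ones, in whom CD19 loss matters most.

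A reader might go further and infer that later therapy will be reported as MOR00208 escape or failed recovery, biasing the answer against later CD19-directed treatment. The documents do not support this. 15.13.9 defines no escape or non-recovery percentage, 15.13.1 says only what later treatment may include, and the direction of any bias depends on an unknown therapy mix. Nor do the protocol's 3.1 and 17.6 months show that new therapy is likely within 7 months of EoT. They are survival after ibrutinib discontinuation and after CLL progression, not time to next therapy after MOR00208.

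**Conclusion.** The point holds in two parts. First, the mutation measure cannot be derived as named, because no genetic sample is scheduled between C1D1 and the post-treatment visits; this follows from the schedule alone and needs no assumption. Second, the written analysis does not separate samples by later therapy, so the effect of that therapy could be mixed into the CD19 loss and recovery summaries. How often this would happen is unknown; the 18% to 80% range at Visit 4 rests wholly on assumed medians of 3 to 24 months. A single misdated case is worth 4.2 to 8.3 points at 24 or 12 evaluable patients.

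The sub-study is optional, exploratory and descriptive, and is reported as an addendum. No primary or secondary endpoint changes. The correction is worth making before the sub-study analysis because it is cheap and bears directly on the sub-study's own question.

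**What to change.** In Protocol 15.13.9 and the sub-study SAP:

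1. **Reword the mutation measure** as a CD19 mutation absent at C1D1 and present in the first post-treatment sample taken before any new anti-tumour therapy or further MOR00208. The denominator is patients who have both samples.
2. **Split the CD19 level and change summaries.** Present them on samples before new anti-tumour therapy or further MOR00208. Beside that, show the all-samples summary, and list the post-therapy samples separately, flagged by therapy type. Showing all three guards against the informative cut.
3. **Confirm the data.** Check that the Laboratory Requisition Form captures therapy type and start date, including therapy begun between EoT and a late entrant's first visit.

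The cost is wording and possibly one added date field; no new samples are needed. The price in information is fewer samples in the pre-therapy summaries at Visits 3 and 4. For example, with 12 patients and an assumed median of 3 to 6 months to new therapy, about 12 × 0.20 = 2.4 to 12 × 0.45 = 5.4 would remain at Visit 4, before any other loss.
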